1.0 Objectives

The overall goal of this proposed study is to increase the capacity for sustainability among evidence-based tobacco control (TC) programs. Although all 50 states have implemented evidence-based TC programs and policies, states vary in their abilities to support and sustain these programs over time. Most states still do not meet the CDC recommended level for funding their TC program allowing for tobacco use to remain the leading cause of preventable disease and death in the US.¹ Also, as part of the 2015 National State-Based Tobacco Control Program Funding Announcement released by the CDC,² all awarded state applicants are “required to develop a sustainability plan” and “provide measures of execution of all activities as outlined in the sustainability plan”. There are currently no available resources specifically designed to help states meet this requirement making this project imperative for states to effectively meet this important funding requisite.

[figure not shown]
- Phase 1 (Aim 1) focuses on refining and finalizing our evidence-based Program Sustainability Action Planning Model and Training Curriculum and deliver to 12 states. The Program Sustainability Action Planning Training will incorporate experiential learning methods³⁻⁶ and includes: action planning workshops, development of action plans with measurable objectives to foster institutional changes, and technical assistance.
- Phase 2 (Aim 2) will use a randomized effectiveness trial to assess the Program Sustainability Action Planning Training in 24 states (12 intervention, 12 comparison). Evaluation of our training program is centered on the theory of change.^{7,8}
- Phase 3 (Aim 3) focuses on responding to study results by making any needed revisions and conduct widespread dissemination of our Program Sustainability Action Planning Model and Training Curriculum starting with the 12 comparison states.

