(Aim 2): Demonstrate change in sustainability outcomes in states who received the Program Sustainability Action Planning training compared to states who did not.

The overall goal for the Program Sustainability Action Planning Training and subsequent dissemination activities is to increase capacity for sustainability of evidence-based state TC programs through the institutionalization of the program. To determine the extent of reaching this goal, we will design a randomized effectiveness trial to document differences in organizational and programmatic measures and Program Sustainability Assessment Tool scores between intervention and comparison states. We will rely on three sources of data for this study: 1) state-level program records for measures of predictors of sustainability and institutionalization,^{9,11} 2) PSAT scores and 3) a key informant interview and survey with state program managers. While we anticipate that our study will impact behavioral risk factors for tobacco-related diseases (e.g., rates of smoking and initiation), the dependent variable for our study involves measures of program institutionalization and sustainability.

C.6.a. Data collection methods

Pre-Introduction to Sustainability Webinar Survey

All participants will receive an optional Qualtrics survey via email, prior to participating in the “Introduction to Sustainability” webinar. Participants will be asked program sustainability perception questions, as well as demographic questions (age, gender, race, per NIH reporting requirements). Personally identifiable information, such as the participant’s name, will not be collected.

Program Sustainability Assessment Tool (PSAT)

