The survey will be conducted online using established methods for Web-based surveys.¹⁰² To enhance the survey response, we will employ the well-established method developed by Dillman.¹⁰³ First, all members of the sample will receive a personalized, advanced notice email. This helps to identify the purpose of the survey and establish its legitimacy. Second, approximately one week after the advance email is sent, all members of the workgroup receive the survey link. In all cases, the replies to the surveys will be anonymous. Third, approximately one week after completion of the PSAT, a follow-up email will be sent to all members of the sample. It will thank those who have already responded and request a response from those who have not yet responded. Finally, once data collection is closed, the workgroup members will receive a detailed sustainability report that includes their responses and an aggregated score for the program. For intervention states, this report will serve in the assessment and planning phases. All correspondence will come from WU and the TCN (an important professional association for our sample). The CDC has also agreed to allow us to participate on the OSH Program Service Branch calls to make CDC program officers aware of their state’s participation and for promotion of our study. We have had previous success with online administration of surveys including the PSAT. Response rate for PSAT administration across the six TC states was 86% (123 out of 143). In another study, in which we administered an email survey among all 50 state TC managers in three waves, with an overall response rate of 97%.^{51,78} In addition, we have years of experience and building partnerships with state TC programs and CDC-OSH.

Program record abstraction

A review and abstraction of state level TC program public records will be performed for all 24 states at three time points- baseline and at the annual CDC progress reporting time (June) in years

2 and 3. This will help in evaluating the impact of the training intervention on the capacity for sustainability and institutionalization of the TC program within the organization.

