To incorporate the influence of idiosyncratic characteristics of the state programs, longitudinal regression analysis will be used to model the outcome for each of the dependent variables. This analysis is modeled in Equation 1.

$$\beta_0 + \beta_1 PSAT_{i,t=0} + \beta_2 G_i + \beta_3 D_{it} + \beta_4 (G_{it} * D_{it}) + B_{5-k} X_{it} = Y_{it}$$

Equation 1

where i = state, t = time 1 or 2, $PSAT_{i,t=0}$ = baseline PSAT score, G_i = group (intervention or comparison), D_{it} = dose variable, $(G_{it} * D_{it})$ = an interaction between the group and dose terms, X_{it} = a vector of programmatic, organizational, community and funder variables, and Y_{it} = the

Figure 4. Sample size and power calculation

outcome variable. This analysis will ultimately be used to test Hypothesis 1, that the impact of the training is nonzero and positive.

$$H_0: \hat{\beta}_{intervention} = 0 \quad H_a: \hat{\beta}_{intervention} > 0$$

Hypothesis 1

The multivariate approach allows us to account for the numerous influences found in programmatic, organizational, community, and funder attributes. Data collection at different time points also allows for measuring changes in these variables, and the influence these changes have on institutionalization outcomes. In addition, the level of adoption and implementation of action plans both from the training (intervention states) and from other initiatives (comparison states) will vary across programs and time. Varying levels of action plan implementation across states must be acknowledged. Multivariate longitudinal analyses also allow us to control for differing degrees of dosage reception and delivery. We have successfully used similar dose variables.^{111,112}

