Data abstraction. State level TC program records will be reviewed and data will be abstracted by two trained evaluators using standardized methods and data collection tools created by the research team. Examples of variables of interest include: implementation of action plan, amount and source of funding allocated for the implementation of tobacco control programs, size of the program and organization, and number of staff dedicated to support programmatic activity. Funding-related information will be collected from annual progress reports of state health departments, annual reports, and funding opportunities of funding agencies relevant to tobacco control. Abstraction will include only records that are publically available and only programmatic and organizational information will be recorded. No individual identifying information will be recorded.

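### Equation 1 tests the training effect while adjusting for follow-up values of state covariates, some of which the training is meant to change, so the group coefficient need not be the total effect of assignment

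*Combined protocol and SAP*

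**What the plan says.** Section 9.0, C.6.e, models each outcome by longitudinal regression (Equation 1). The terms are baseline PSAT, group G, dose D_it, a group-by-dose interaction, and X_it, described as "a vector of programmatic, organizational, community and funder variables". The index is defined as "where i = state, t = time 1 or 2", and the PSAT covariate is the only term marked t=0. The text after the equation confirms that follow-up values are intended: "Data collection at different time points also allows for measuring changes in these variables, and the influence these changes have on institutionalization outcomes".

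The same model carries the trial's test: "This analysis will ultimately be used to test Hypothesis 1, that the impact of the training is nonzero and positive". No version without X, or with X at baseline only, is described.

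Other sections say what the training should move:

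- Section 1.0 Objectives includes in the training the "development of action plans with measurable objectives to foster institutional changes".
- Section 5.1, Phase 2 (Aim 2), says the trial is to "document differences in organizational and programmatic measures and Program Sustainability Assessment Tool scores between intervention and comparison states".
- The rationale in section 1.0 cites earlier work in which sustainability planning predicted later funding, and action-planning training was followed by greater infrastructure capacity.
- Section 10.0, Data abstraction, gives examples of abstracted variables: "implementation of action plan, amount and source of funding allocated for the implementation of tobacco control programs", followed by program and organization size and staff numbers.

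**The concern.** Randomisation protects the comparison of states as assigned. It does not protect a comparison made at equal values of something measured after training began. If training brings a state more funding or staff, and these strengthen institutionalization, then holding follow-up funding and staffing fixed takes that route out of the group coefficient. What is left is a partial effect. If follow-up X and the outcome also share unmeasured causes, such as a change in the state's political climate, conditioning on X can add bias in either direction.

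At stake is the meaning of Hypothesis 1. Training that worked largely through funding or staffing could show a small group coefficient, and the model would not reveal why.

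**Working it through.** **Step 1: does X hold follow-up values?** Yes. The subscript is it, t is 1 or 2, the baseline PSAT is explicitly marked t=0, and the text speaks of changes in these variables.

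**Step 2: can training change X?** The available text does not list X. Funding, program size and staffing are plausible members, inferred from the abstraction examples in section 10.0. The link to training is explicit for programmatic and organizational measures (section 5.1). It is less direct for funder variables (the cited planning-to-funding evidence, and the PSAT funding domain) and for community variables (the PSAT partnership domain). Some items cannot be affected: how long the program has existed, an example question in the manager interview, is one.

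**Step 3: reproduce the plan's figure.** Inputs from section 9.0, C.6.d: effect 1.25 SD, power 0.8, alpha 0.05, about 9 per group calculated, 12 planned. A two-sample t-test (noncentral t) gives:

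- one-sided: n = 8.68, so 9 per group, which reproduces the plan; power at 12 per group is 0.91;
- two-sided: n = 11.09, so 12 per group; power at 12 per group is 0.83.

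The power text does not state sidedness. The one-sided basis is inferred from this match and from the one-sided alternative in Hypothesis 1.

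**Step 4: effect on the coefficient.** Let m be the share of the total effect that runs through X. With no unmeasured common causes:

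adjusted coefficient = 1.25 × (1 − m)

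- m = 0.25: 1.25 × 0.75 = 0.9375, about 0.94 SD
- m = 0.50: 1.25 × 0.50 = 0.625, about 0.63 SD

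The documents do not give m, so both values are assumptions. A simulation of 24 states with one follow-up agrees: mean coefficients were 0.93 and 0.62 when adjusting for follow-up X, and 1.24 to 1.25 when adjusting for baseline X or for no X.

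**Step 5: effect on power.** This needs a second assumption, the coefficient b of X on the outcome. Set the within-group SDs of X and of the outcome to 1. Training then shifts X by 1.25m/b, and the residual SD of the outcome is √(1 − b²). Simulated two-sided power at 12 per group:

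| Share through X | Coefficient | b = 0.3 | b = 0.6 | b = 0.8 |
|---|---|---|---|---|
| 25% | 0.94 SD | 0.51 | about 0.73 | 0.93 |
| 50% | 0.63 SD | 0.18 | about 0.35 | 0.61 |

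The unadjusted comparison has 0.83. At 25% with b = 0.8, power exceeds that, because X also absorbs outcome variance (residual SD √(1 − 0.64) = 0.6). The shrinkage of the coefficient does not depend on b; the power does.

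**Step 6: are baseline values available?** Yes. Records are abstracted at "baseline and at the annual CDC progress reporting time (June) in years" 2 and 3, and manager interviews also have a baseline round. The selection quadrants and FY2015 funding percentage are defined before allocation (section 3.0).

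**The case against.** The sponsor can fairly say that X is there to account for differences between states, that its contents are not known to be consequences of training, and that group-by-time comparisons of the dependent variables are also planned in C.6.e. Part of this stands. The examples in section 10.0 are never assigned to X, and some may be outcomes. The protocol refers to an appendix linking reporting requirements to predictors and outcomes, but that mapping is not in the text available here. X items that training cannot change cause no bias. The unadjusted comparisons would be seen, although Hypothesis 1 is not tested on them. None of this justifies follow-up values: baseline values account for state differences without the problem.

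Three stronger readings are tempting and should not be adopted.

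- *Action-plan implementation is the clearest mediator in X.* It appears among the abstraction examples, but section 10.0 defines dosage received by it, so it belongs with D_it and the separate dose problem.
- *The estimate is certainly biased toward zero, with one known power loss.* The direction is conditional and, as the table shows, the power result turns on an assumed coefficient.
- *The number of covariates alone wrecks power.* With 4, 8 or 12 covariates that explain nothing, two-sided power would be about 0.75, 0.63 or 0.48. But the number is not stated and this is the worst case: four covariates explaining 30% of outcome variance would give about 0.87.

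**Conclusion.** The concern holds in conditional form. As written, the one model that tests Hypothesis 1 conditions on follow-up variables in categories the protocol itself expects training to improve. For each X item that training changes, the group coefficient is not the total effect of assignment. On the protocol's own theory (training raises X, X raises the outcome) it is too small; with shared unmeasured causes the bias could go either way.

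The size cannot be computed from the documents. The reductions to about 0.94 and 0.63 SD rest on assumed shares of 25% and 50%, and the power ranges also on coefficients of 0.3 to 0.8. A reader might infer that training would be declared ineffective; the documents do not support that as a prediction, only as a possibility that the model leaves open.

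Nor does correcting X suffice. D_it and the group-by-dose term are also measured after randomisation, and while they remain, the group coefficient is still not the effect of being offered the training.

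**What to change.** In the model that tests Hypothesis 1:

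1. Replace X_it by a short prespecified set measured before training and before assignment is disclosed: the baseline value of the outcome, the stratification quadrant, and FY2015 funding as a percentage of the CDC recommendation. Disclosure is the right cut-off because section 3.0 has states learn their group after the PSAT, while section 4.0 has workgroups formed after states are divided. For record- and interview-based outcomes, state that the baseline value also predates disclosure; the plan says so only for the PSAT.
2. Remove D_it and the group-by-dose interaction, so that the group coefficient can be read as the effect of being offered the training.
3. Move follow-up X_it to a separate analysis labelled exploratory mediation, with its items listed and its no-unmeasured-confounding assumption stated. This keeps the sponsor's interest in how changes in these variables influence institutionalization.

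The cost is analysis-plan wording only. No new data or states are needed, and the group-by-time descriptive comparisons in C.6.e stay as planned.

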10.0 Recordkeeping

The Principal Investigator, [name], will be responsible for monitoring the data safety and quality of the overall study. This is a minimal risk study that does not warrant a formal Data Safety Monitoring Board.

Program Sustainability Assessment Tool (PSAT). The PSAT is a 40-item measure of a program's sustainability capacity which requires 10-15 minutes to complete. Individuals selected by state TC program managers will be invited to complete the PSAT online via our secure website <https://sustaintool.org/>. Data collected through the website is automatically de-identified by the website and aggregated at the state level. E-mail addresses are collected on the site, but solely for website management, technical assistance, and user access. See Appendix A for full copy.

Workshop Data Collection Form. Several process measures will be collected to assess the effectiveness of the training and support delivered. All measures will be collected via survey at the completion of each training component or tracked by review of programmatic records (i.e., action plan, meeting minutes). Quantitative data collected for this aim will be analyzed using descriptive statistics. Qualitative analysis of programmatic records will be conducted following procedures outlined. See Appendix B for full copy.

Dosage delivered is the number of units of an intervention delivered or provided.¹⁰¹ For this study, this measure will be defined by the number of hours of training and technical assistance provided to each state.

Dosage received is the extent to which participants engage with or use the materials provided.¹⁰¹ This will be measured by whether or not the action plan is completed and implemented, whether the workgroup utilizes the resources and materials provided, and the extent to which the action plan is implemented.

Participant reactions will be measured by the extent to which the participants felt that the objectives of the training and technical assistance were achieved, satisfaction with the training and technical assistance and perceived usefulness of the training provided.

Data abstraction. State level TC program records will be reviewed and data will be abstracted by two trained evaluators using standardized methods and data collection tools created by the research team. Examples of variables of interest include: implementation of action plan, amount and source of funding allocated for the implementation of tobacco control programs, size of the program and organization, and number of staff dedicated to support programmatic activity. Funding-related information will be collected from annual progress reports of state health departments, annual reports, and funding opportunities of funding agencies relevant to tobacco control. Abstraction will include only records that are publically available and only programmatic and organizational information will be recorded. No individual identifying information will be recorded.

Furthermore, the Prevention Research Center has developed a safety monitoring plan to address: 1) training staff on data sensitivity and protocols for safeguarding confidentiality; 2) storing and processing data in a secured, centralized location; 3) securing any hardcopy data in locked files when not in use; 4) removing names, addresses, and other direct identifiers from hardcopy and computer-readable data when they are no longer necessary for respondent tracking and then using encrypted codes for subsequent identification of participants; 5) destroying all identifiable linkages to data after data accuracy has been verified and final analyses have been completed; 6) using restricted logon identification and password protection computer protocols for all computerized entry, retrieval, and analysis; 7) ensuring that the research team members and others with direct contact with participants and/or access to identifiable data complete human research certification (e.g., CITI, and other human research training programs); 8) including human research concerns as a standard agenda item for regular project meetings; 9) incorporating responsibility for the human research protection process into the Project Manager's job description; and 10) regular review of research data to ensure validity. All data will be stored on a section of the Washington University in St. Louis password protected server protected by the university's firewalls. The only people who will have access to the raw survey data are the study staff and faculty based at the Washington University in St. Louis. Each has taken the CITI training and will be approved by the Washington University Institutional Review Board for this specific study.

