3.0 Selection of Participants – Eligibility Criteria

Recruitment. A total of 24 state TC programs will be recruited to participate in this study. We believe this number is feasible for three main reasons: (1) this training will be in high demand because of the CDC’s requirement for all state TC programs to complete a sustainability plan; (2) our strong relationships and past success in evaluating state level TC programs; (3) our project consultant’s 20+ years working directly with state level tobacco programs ([name]).

State selection. We will recruit 24 states, and then randomly assign each state into intervention and comparison conditions. To ensure that both the intervention and comparison groups are equally diverse in terms of organizational factors relevant to tobacco control, we will stratify states using the following three criteria: (1) tobacco control policy progress, (2) smoking rates, and (3) funding for TC program. Tobacco control policy progress is operationalized as the American Lung Association's (ALA) 2015 Smoke-free Score for each state.⁸⁸⁻⁹⁰ The ALA "grades" each state annually according to the comprehensiveness of its smoke-free policies (higher scores indicate more comprehensive smoke-free policies). 2013 adult smoking rates are used for smoking rates⁹⁰ and funding is measured as the actual amount spent on tobacco control as a percentage of the CDC-recommended amount of spending for FY2015.^{88,91} Together, these three indicators characterize states' needs (smoking rates), inputs (funding), and environments (policy). States will also be chosen based on willingness to participate and receipt of prior sustainability training. Figure 3 is divided into quadrants by the median smoking rate and median Smoke-free Score. The size of the circles within each quadrant represents the varying levels of funding. The quadrants delineate the primary selection guidelines. Six states from each quadrant representing varying levels of funding will be randomly assigned to either the intervention or comparison group. This process will guard against selecting a disproportionate number of well- or poorly-funded programs for each group. Furthermore, it will ensure both the intervention and comparison groups are evenly varied in terms of needs and policy environments. All participants in this study are aged 18 years or older. States agreeing to participate in the study will learn of their group assignment after completing the PSAT.

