9.0 Statistical Considerations

C.6.d Statistical power

To estimate the sample size needed for the study, an a priori power analysis was performed using data from a natural experiment. The data consists of Pre and Post PSAT averages from previous work with five tobacco control programs that received action planning and training, and five programs that did not receive action planning or training for which pre- and post-PSAT scores are available. To determine effect size, t-tests of differences-in-means were conducted for the two groups using the changes in PSAT scores between the Pre and Post PSAT data. The standardized differences and t-statistics yielded an effect size of 1.25, which is a large effect size according to Cohen's criteria.¹⁰⁷ Using R statistical environment with packages from Del Re¹⁰⁸ and Champely,¹⁰⁹ the effect size with power = 0.8 and $\alpha = 0.05$ project the necessary sample size to be approximately 9 (programs) per group. Since these calculations are based on a natural experiment, which we note occurred over a period of time that also saw changes to the recommended action planning,² we are careful not to overstate the anticipated power and therefore conservatively propose a sample size one-third larger than calculated, 12 per group as shown in Figure 4. This sample is also sufficient to measure the main goal of the study, to discern whether the training, and accompanying PSAT tool, significantly increase institutionalization of state TC programs.^{108–110}

C.6.e. Data analyses. Descriptive statistics will be calculated (e.g., frequencies and measures of central tendency and dispersion), for both the intervention and comparison group at each of the three data collection time points to assess baseline averages and changes. Multiple comparisons across groups and times will be drawn for independent and dependent variables. All continuous measures will be examined for non-normality and all relationships will be examined for linearity where applicable. Strategies for addressing issues encountered will be applied as necessary such as different functional forms, category scaling, and robust error calculations. In addition, the dose reception and delivery, and participant measures from Aim 1 (C.5.d.) will be used to calculate rates of adoption and implementation of training recommendations (intervention states) and other potential actions taken (comparison states, C.5.e).

[figure not shown]

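### Equation 1 adjusts every outcome for baseline PSAT only, so a record-based outcome is modelled without its own baseline and on a scale left open, which could cost much precision with 24 states

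*Combined protocol and SAP*

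**What the plan says.** **Model (9.0, C.6.e).** The plan states that "longitudinal regression analysis will be used to model the outcome for each of the dependent variables". Equation 1 covers follow-up times 1 and 2. It contains one term fixed at time 0, the "baseline PSAT score", together with group, dose, their interaction, and a time-indexed vector X of programmatic, organizational, community and funder variables whose members are not listed.

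**Scale (9.0, C.6.e).** Group-wise descriptive statistics at all three time points come first, followed by checks of normality and linearity. Then: "Strategies for addressing issues encountered will be applied as necessary such as different functional forms, category scaling, and robust error calculations". No rule is given for which remedy applies when.

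**Record measures (10.0, Data abstraction).** The list opens with "Examples of variables of interest include" and includes "amount and source of funding allocated for the implementation of tobacco control programs, size of the program and organization, and number of staff". No percentage, per-capita, log or change-from-baseline definition accompanies them.

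**Role of the records.** Section 5.1 (Aim 2) uses "state-level program records for measures of predictors of sustainability and institutionalization", without saying which variables fall on which side. Its paragraph on record abstraction schedules it at baseline and twice later, and gives its purpose as evaluating the effect of the training.

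**Existing funding measure (3.0, State selection).** There, "funding is measured as the actual amount spent on tobacco control as a percentage of the CDC-recommended amount of spending for FY2015". It is used to select and stratify states and is not carried into C.6.e.

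**The concern.** When the outcome is the PSAT score, Equation 1 has the right baseline term. When the outcome is a record measure, the same equation adjusts for the baseline of a different variable. State programs may differ far more from one another in funding or staffing than any one of them changes over two years. In that case most of the variance of an unadjusted follow-up value is stable between-state difference, and the measure's own baseline would remove it.

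The open scale adds to this. Raw amounts are likely to be skewed across states, and the plan meets that by choosing a functional form or categories once the data have been looked at, with group summaries already in hand and no masking of the analyst stated.

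At stake is the ability of 24 states to show an effect on the measures that do not rest on self-report. Section 9.0 asserts that the sample also suffices for institutionalization but gives no variance or effect size for any record measure.

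**Working it through.** **1. The plan's own figure.** Section 9.0 states an effect size of 1.25, power 0.8 and alpha 0.05, giving about 9 programs per group, raised to 12. Two-sample t-test power uses the noncentral t with 2n − 2 degrees of freedom and noncentrality d·√(n/2).
- One-sided alpha 0.05, n = 9: power 0.814. The stated 9 is reproduced.
- Two-sided, n = 9: power 0.702, and 12 per group would be needed.
- At 12 per group: 0.907 one-sided, 0.833 two-sided.

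This concerns change in PSAT score. It says nothing about funding, staff or size. Hypothesis 1 has a one-sided alternative, so one-sided tests are used below.

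**2. Assumptions for a record outcome (none is given in the documents).** Amount = state size × funding level × random change × training effect, all lognormal. Training effect +30%; SD of log change 0.25; log-SD of level 0.6; log-SD of size 0.8 to 1.2; 12 v 12; one follow-up; ordinary least squares at one-sided 0.05. Dose, X and baseline PSAT are left out, which treats them as unrelated to the outcome.

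**3. Why the own baseline matters, on the log scale.** The effect is log 1.3 = 0.262.
- Without baseline, at size SD 1.0: SD = √(1.0² + 0.6² + 0.25²) = 1.193; d = 0.262/1.193 = 0.22; noncentrality 0.22 × √6 = 0.54; power about 13%.
- With log baseline: residual SD 0.25; d = 0.262/0.25 = 1.05; noncentrality 1.05 × √6 = 2.57; power about 80% before the small loss from chance baseline imbalance. Simulation gives about 78%.

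**4. Simulated power, same assumptions.**

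| Analysis of the outcome | Size SD 0.8 to 1.2 |
|---|---|
| Raw amount, no own baseline | about 12% falling to 8% |
| Raw amount, own baseline | about 55% falling to 45% |
| Percentage of recommended, no baseline | about 21–23% |
| Percentage of recommended, own baseline | about 68% |
| Log amount, log baseline | about 78% |
| Log percentage, log baseline | about 78% |

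The denominator alone moves power from about 10% to about 22%. The own baseline alone moves it from about 10% to about 50%. Once the outcome and its baseline are logged, the denominator adds nothing.

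**5. Second set of assumptions.** Effect +25%, SD of log change 0.2, level SD 0.5, size SD 0.3 to 1.2:
- raw amount, no baseline: 0.20 falling to 0.08
- raw amount with size as covariate: 0.23 falling to 0.15
- raw amount with own baseline: 0.73 falling to 0.50
- percentage without baseline: about 0.24; with own baseline: about 0.75
- log amount with log baseline: about 0.82

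The order is the same.

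**6. Error rate under no effect.** Rejection was 0.04 to 0.05 on every fixed scale. The loss is of precision; the test stays valid.

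**The case against.** **The variables may not be outcomes.** Section 10.0 calls them examples of variables of interest, X in Equation 1 holds variables of this kind, and section 9.0 speaks of the influence of their changes on institutionalization. Appendix C, cited in 5.1 as linking reporting requirements to predictors and outcomes, is not in the text available. This stands: the point applies only where a record measure is used as a dependent variable. It does not remove the point, because 5.1 names the records as a source for institutionalization and evaluation of the training as the reason for abstracting them.

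**X may already handle size.** It may, but size as a covariate reached only 0.15 to 0.23 in step 5. X is also indexed at the follow-up times, so as written it does not supply the outcome's baseline.

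**Abstraction is not analysis.** Dollars must be recorded before a percentage can be formed, so the list in 10.0 does not commit the plan to raw units. That is fair. The gap is that no scale is stated.

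**Stronger readings a reader might infer.**
- That state size swamps these measures, or that they are nearly uninformative in raw units. No variance in the documents supports the first, and 45–55% power with own baseline contradicts the second.
- That the open scale raises type I error to about 8%. That figure assumes taking the smallest of four p-values. The plan describes remedies prompted by diagnostics; one such rule (log both when raw residuals fail a normality test) gave 5.7% type I error and 74% power on the step 2 assumptions.
- That a permutation test is required. On normal data it matched the t-test (0.905 v 0.907), and no gain on skewed data has been shown.

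**Conclusion.** The concern holds as one of precision and pre-specification. For any record-based outcome, Equation 1 omits the most useful covariate, although the records are abstracted at baseline, and C.6.e does not fix the scale. Under the assumed values, a raw amount without its own baseline has about 8–12% power. The own baseline brings it to 45–55%, and the log scale with log baseline to about 78%.

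The treatment comparison is not biased, because states are randomised and every fixed scale kept its error rate. The exact figures rest on assumed lognormal variances and on baseline PSAT being unrelated to the record measure; if it were strongly related, the loss would be smaller. The ranking of the analyses was the same under both sets of assumptions. The percentage measure in section 3.0 is a sensible scale for funding, but its absence from C.6.e is not the main source of the loss, and it covers neither staff nor program size.

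**What to change.** In C.6.e:
1. State which record variables are outcomes and which are covariates in X.
2. For each record-based outcome, replace baseline PSAT in Equation 1 with that outcome's own baseline value, or add it alongside.
3. Analyse positive amounts and counts on the log scale with log baseline. For funding, the percentage of the CDC-recommended amount from section 3.0, with its own baseline, is an acceptable alternative.
4. Settle any other transformation or cut-point on baseline data, before follow-up data are joined to arm.

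This needs only plan wording, since the baseline abstraction is already scheduled. Keeping baseline PSAT as well uses one more degree of freedom out of 24 states. The small downside is that effects are read as ratios, not as dollars or head-counts.
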